### 3. PARTICIPANT SELECTION

#### 3.1 Eligibility Criteria

Participants must meet the following criteria on screening examination to be eligible to participate in the study:

- 3.1.1 Participants must have histologically or cytologically confirmed stage IV or recurrent non-small cell lung cancer with a documented exon 20 insertion mutation in *EGFR* (exon 20 insertion/deletion and deletion mutations will also be allowed)
- 3.1.2 Participants must have measurable disease by RECIST 1.1
- 3.1.3 Patients must have received at least one prior line of therapy for their advanced lung cancer but there is no restrictions on the maximum number of prior therapies allowed.
- 3.1.4 Age  $\geq$  18 years.
- 3.1.5 Life expectancy  $\geq$  12 weeks.
- 3.1.6 ECOG performance status  $\leq$  2 (see Appendix A)
- 3.1.7 Participants must have normal organ and marrow function as defined below:
  - Hematologic:
    - Absolute Neutrophil Count (ANC)  $\geq 1.5 \times 10^9/L$
    - Hemoglobin (Hgb)  $\geq 8 \text{ g/dL}$
    - Platelets (plt)  $\geq 100 \times 10^9/L$
  - Biochemistry:
    - Potassium within normal limits or correctable with supplements
    - Magnesium  $>$  LLN or correctable with supplements
    - Calcium (after correction for albumin level)  $>$  LLN or correctable with supplements
  - Liver and Kidney Functions
    - AST/SGOT and ALT/SGPT  $\leq 3.0 \times$  Upper Limit of Normal (ULN) or  $\leq 5.0 \times$  Upper Limit of Normal (ULN) if liver metastases are present
    - Serum bilirubin  $\leq 1.5 \times$  ULN
    - Serum creatinine  $\leq 1.5 \times$  ULN or 24-hour clearance  $\geq 50 \text{ ml/min}$

3.1.8 The effects of AUY922 on the developing human fetus are unknown. For this reason women of child-bearing potential and men must agree to use adequate contraception (hormonal or barrier method of birth control; abstinence) prior to study entry and for the duration of study participation. Should a woman become pregnant or suspect she is pregnant while participating in this study, she should inform her treating physician immediately. In addition, women of child-bearing potential must have a documented negative serum pregnancy test. The serum pregnancy test must be obtained prior to the first administration of AUY922 ( $\leq$  72 hours prior to dosing) in all pre-menopausal women and women  $<2$  years after the onset of menopause.

3.1.9 Ability to understand and the willingness to sign a written informed consent document.

3.1.10 Patients must have a normal baseline ophthalmologic examination or have only clinically-insignificant abnormalities. Patients with significant visual/ocular abnormalities identified during the baseline eye exam may be eligible after discussion with the study PI and it is thought that the abnormalities pose no increased risk with study therapy.

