## 3.2 Exclusion Criteria

Participants who exhibit any of the following conditions at screening will not be eligible for admission into the study.

3.2.1 Participants may not have had other anti-neoplastic therapies within the following timelines:

- Radiation within 2 weeks
- Cytotoxic chemotherapy or monoclonal antibodies within 2 weeks, if all treatment-related toxicities have resolved to  $\leq$  grade 1 prior to starting study treatment.
- EGFR tyrosine kinase inhibitor within 2 weeks
- Any other small molecule inhibitor within 2 weeks or 5 half-lives of the compound, whichever is shorter
- Experimental treatment of any type within 30 days

3.2.2 Participants may not be currently receiving any other experimental agents.

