#### 9.1.1 Disease Parameters

**Measurable disease.** Measurable disease is the presence of at least one (1) lesion that can be accurately measured in at least one dimension with longest diameter  $\geq 20$  millimeters (mm) using conventional techniques (CT, MRI, x-ray) or  $\geq 10$  mm with spiral CT scan. Measurable lesions must be at least 2 times the slice thickness in mm. All tumor measurements must be recorded in millimeters (or decimal fractions of centimeters).

**Reminder:** A lesion in a previously irradiated area is not eligible for measurable disease unless there is objective evidence of progression of the lesion prior to study enrollment. Lesions in previously irradiated areas must be clearly identified as such.

**Malignant lymph nodes.** To be considered pathologically enlarged and measurable, a lymph node must be  $\geq 15$  mm in short axis when assessed by CT scan (CT scan slice thickness recommended to be no greater than 5 mm). At baseline and in follow-up, only the short axis will be measured and followed.

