#### 9.1.4 Duration of Response

**Duration of overall response:** The duration of overall response is measured from the time measurement criteria are met for CR or PR (whichever is first recorded) until the first date that recurrence or PD is objectively documented, taking as reference for PD the smallest measurements recorded since the treatment started.

**Duration of overall complete response:** The duration of overall CR is measured from the time measurement criteria are first met for CR until the first date that recurrent disease is objectively documented.

**Duration of stable disease:** Stable disease is measured from the start of the treatment until the criteria for progression are met, taking as reference the smallest measurements recorded since the treatment started.

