## 13.2 Sample Size/Accrual Rate

A Simon two-stage design will be used. In this design we will consider a rate of response plus SD lasting  $\geq 3$  months that is no greater than 5% as evidence that AUY922 is ineffective as a monotherapy in patients with exon 20 insertion mutations in *EGFR*, and 20% will be the target rate of effectiveness. In other words,  $H_0=0.05$  and  $H_a=0.20$ .

This design requires that 10 patients will be initially enrolled (the first stage of the Simon design). If there are no responses or patients with SD lasting  $\geq$  3 months in these 10 patients then AUY922 will be considered ineffective in *EGFR* exon 20 insertion mutation patients. If at least 1 PR or SD lasting  $\geq$  3 months is noted, then an additional 19 patients will be enrolled (the second stage of the Simon design).

If the total number of responses plus SD lasting  $\geq$  3 months in the entire set of 29 patients is 4 or more, then AUY922 will be considered for further evaluation, likely in a randomized setting. If the number of responses of PR or SD lasting  $\geq$  3 months is 3 or fewer in the entire set of 29 patients, then AUY922 will be considered potentially ineffective and further investigation may be unwarranted.

Using this design, if AUY922 is actually not effective, there is a 0.047 probability of concluding that it is (the target for this value was 0.050, the  $\alpha$ -level). If the drug is actually effective, there is a 0.199 probability of concluding that it is not (the target for this value was 0.200, the beta-level [80% power]). The power and  $\alpha$ -level are slightly different from the nominal values due to the discrete nature of the binomial distribution of response.

Among the three participating clinics (MGH, DFCI and BIDMC), we expect to enroll approximately 1.5 patients per month. Therefore, assuming full enrollment to 29 patients, accrual should be complete within 20 months.

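### Stable disease of 3 months or more counts as a success at both stages, but entry does not require progression, so disease that was not growing can be scored as AUY922 activity.

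*Combined protocol and SAP*

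**What the plan says.** **Entry.** Section 3.1.1 states that "Participants must have histologically or cytologically confirmed stage IV or recurrent non-small cell lung cancer", with a documented exon 20 mutation. Section 3.1.2 requires measurable disease by RECIST 1.1. On earlier treatment, 3.1.3 says "Patients must have received at least one prior line of therapy for their advanced lung cancer" and sets no upper limit on the number of lines. The first group of exclusions (3.2.1) is a set of washout periods. One bars "Cytotoxic chemotherapy or monoclonal antibodies within 2 weeks", and an EGFR TKI has the same 2-week limit.

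**Progression before entry.** No item in 3.1.1 to 3.1.10 or 3.2.1 to 3.2.14 asks for it at patient level. The progression conditions in section 9.1.1 concern single lesions. A lesion in an irradiated field does not count as measurable "unless there is objective evidence of progression of the lesion prior to study enrollment", and the target-lesion paragraph says much the same of lesions given other loco-regional therapy.

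**Decision rule.** Section 13.2 sets the null with the words "In this design we will consider a rate of response plus SD lasting" 3 months or more, at no greater than 5%, and adds that "20% will be the target rate of effectiveness". The trial continues after 10 patients if at least one succeeds, and AUY922 goes forward if at least 4 of 29 succeed. The stated errors are 0.047 and 0.199. By section 9.1.4, "Stable disease is measured from the start of the treatment until the criteria for progression are met".

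**The concern.** Shrinkage of 30% or more seldom happens unaided, so a response is reasonable evidence of activity whatever the tumour was doing at entry. Stable disease is different. It points to drug activity only if the disease would otherwise have grown within the period counted.

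The entry criteria do not secure that. A patient who finished chemotherapy three weeks ago with disease under control, or who has slow-growing disease and is on a treatment break, can meet every listed criterion. If that patient remains without progression for 3 months from the start of treatment, section 13.2 counts a success. There is no control arm to show that the same would have happened without AUY922.

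One such patient among the first 10 is enough to open stage 2, and four among 29 are enough for a go. At stake is the false-positive rate of the trial's decision rule, which the plan states as 0.047.

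**Working it through.** **Inputs from section 13.2:** stage 1 n = 10, continue if at least 1 success; stage 2 adds 19; go if at least 4 of 29; null 5%, target 20%.

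**Formula.** For a true success rate p,

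P(go) = Σ over x = 1 to 10 of P[Bin(10, p) = x] × P[Bin(19, p) ≥ 4 − x], the second factor being 1 when x ≥ 4.

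P(pass stage 1) = 1 − (1 − p)^10.

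**Step 1: reproduce the plan.** At p = 0.05:

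- x = 1: 0.3151 × 0.0665 = 0.0210
- x = 2: 0.0746 × 0.2453 = 0.0183
- x = 3: 0.0105 × 0.6226 = 0.0065
- x ≥ 4: 0.0010

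The sum is 0.0468, the stated 0.047. At p = 0.20, P(go) = 0.8011, so beta = 0.1989, the stated 0.199. The design arithmetic is right.

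**Step 2: what p means for an inactive drug.** It is the proportion of enrolled patients who would be scored as successes with no drug effect. Suppose a fraction f of entrants are not progressing and stay stable for at least 3 months with probability q, while the rest succeed at the null rate of 5%. Then

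p = 0.05 × (1 − f) + q × f.

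Both f and q are assumptions; the documents give neither.

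| f | q | p | P(pass stage 1) | P(go), inactive drug |
|---|---|---|---|---|
| 0 | – | 5.0% | 0.401 | 0.047 |
| 5% | 30% | 0.0475 + 0.015 = 6.25% | 0.476 | 0.090 |
| 10% | 30% | 0.045 + 0.03 = 7.5% | 0.541 | 0.147 |
| 10% | 50% | 0.045 + 0.05 = 9.5% | 0.631 | 0.258 |
| 20% | 50% | 0.04 + 0.10 = 14% | 0.779 | 0.534 |

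In the mildest non-zero row, f = 5% is about 1.5 patients in 29 (0.05 × 29 = 1.45), and the false-go probability nearly doubles.

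**Step 3: would requiring progression restore 0.047?** Only if progressing patients on an inactive drug succeed at 5% or less, which the first row assumes. If their background rate were instead 15% (again an assumption), P(go) would be 0.589 with no non-progressing entrants. With f = 10% and q = 50%, p = 0.15 × 0.9 + 0.05 = 18.5% and P(go) = 0.749. For scale, under an assumed exponential PFS, 5% progression-free at 3 months implies a median of 3 × ln 2 / ln 20 = 0.69 months.

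**The case against.** The strongest reply is that the size is assumed. The documents show that non-progressing patients are permitted, not that they would be enrolled in numbers. With f near zero the error stays at 0.047. This stands: the gap in the text is certain, while its effect is a range.

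Second, entry may not be the main weakness. Step 3 shows that a 5% null for an endpoint that includes SD could be too low even among progressing patients. This also stands. A reader might infer that adding a progression requirement would make the stated alpha sound; nothing in the available text supports that. The text of section 2.3 (Rationale) was not available for this review, so a justification of the 5% there cannot be ruled out. It would not alter the entry criteria.

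Third, the consequences are bounded. A reader might infer that the reported response rate is inflated too. It is not: section 13.6 reports response by RECIST, in which SD is not a response. A go leads only to further evaluation, probably randomized, where a control could expose background stability. That softens the error but does not remove it.

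Fourth, it may be said that investigators would in practice enrol only progressing patients. The protocol does not require it, and section 4.2 registers patients against the listed criteria.

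One further tempting reading is that flat scans at weeks 6 and 12 make a success. Twelve weeks is 84 days, short of 3 months, and scans are timed from registration while SD runs from the start of treatment. Later follow-up is needed.

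**Conclusion.** The concern holds as a weakness in how entry supports the decision rule. Sections 3.1 and 3.2 admit patients whose disease was not progressing, and section 13.2 can score their stability as AUY922 activity at both stages. The alpha of 0.047 is conditional on a drug-independent success rate of at most 5%, which the entry criteria do nothing to secure.

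Across the assumed rates of 6.25% to 14%, the false-go probability runs from 9% to 53%. These figures show how sensitive the rule is; they do not estimate what would happen in this trial. The primary objective, overall response rate, is estimated without SD, and the consequence of a go is further study. For those reasons this is should-fix rather than must-fix. It belongs with the wider question of how the 5% null was chosen.

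**What to change.** Amend 3.1.3 to require at least one prior line for advanced disease together with documented radiographic progression on or after the most recent systemic therapy, or after stopping that therapy for intolerance. Record the date of that progression on the On Study Form.

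For patients already enrolled without it, leave the 13.2 rule as it stands. As a sensitivity analysis, report the success count with and without their SD. Dropping SD for some patients within the rule itself would make the definition of success depend on the patient, in an open-label trial, and the stated 5% and 20% hypotheses and 80% power would no longer apply.

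The cost is one eligibility sentence and one date field. Patients on a treatment break would wait until imaging shows progression, which may mean imaging before entry that they would not otherwise have had then. Accrual, planned at about 1.5 patients per month, may be slightly slower. The basis for the 5% null still needs to be stated separately.

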### **4.2 Registration Process for DF/HCC and DF/PCC Institutions**

The QACT registration staff is accessible on Monday through Friday, from 8:00 AM to 5:00 PM Eastern Standard Time. In emergency situations when a participant must begin treatment during off-hours or holidays, call the QACT registration line at [REDACTED] and follow the instructions for registering participants after hours.

The registration procedures are as follows:

1. Obtain written informed consent from the participant prior to the performance of any study related procedures or assessments.
2. Complete the protocol-specific eligibility checklist using the eligibility assessment documented in the participant's medical/research record. **To be eligible for registration to the study, the participant must meet each inclusion and exclusion criteria listed on the eligibility checklist.**

**Reminder:** Confirm eligibility for ancillary studies at the same time as eligibility for the treatment study. Registration to both treatment and ancillary studies will not be completed if eligibility requirements are not met for all studies.

3. Fax the eligibility checklist(s) and all pages of the consent form(s) to the QACT at [REDACTED]

**Exception:** DF/PCC Affiliate sites must fax the entire signed consent form including HIPAA Privacy Authorization and the eligibility checklist to the Network Affiliate Office. The Network Affiliate Office will register the participant with the QACT.

4. The QACT Registrar will (a) validate eligibility, (b) register the participant on the study, and (c) randomize the participant when applicable.
5. The QACT Registrar will send an email confirmation of the registration and/or randomization to the person initiating the registration immediately following the registration and/or randomization.

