## **5.1 Pre-treatment Criteria**

### **5.1.1 Cycle 1, Day 1**

The patient should continue to meet all eligibility criteria on C1D1, as they did during the screening period.

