| Survival   |                |         |   |   |         |    |   |                   |    |                 |                  |                     | X                     | X                         | X            |     |
| Tumor sample for mutation and amplification testing  | X              |         |   |   |         |    |   |                   |    |                 |                  |                     | X                     | X                         | X            |     |

1. Vital signs – During treatment period, vital signs will be performed pre-dose (including temperature, respiratory rate, blood pressure, pulse, weight and ECOG PS) and immediately post-dose infusion (including temperature, respiratory rate, blood pressure and pulse).
2. ECG- Please refer to Table 3 for detailed schedule of ECGs.
3. In women of child-bearing potential, a serum pregnancy test must be obtained prior (within 14 days) to the first administration of AUY922. CHEMISTRY: BUN, Creatinine, Glucose, Total Protein, Albumin, AST/SGOT, ALT/SGPT, Total Bilirubin, Alkaline Phosphatase, Magnesium, Calcium, Sodium, Potassium, Phosphorous. HEMATOLOGY: CBC with differential
4. Standard ophthalmologic assessments will be required at baseline and follow-up exams will be conducted at the time when visual symptoms are reported (if any), at cycle 3 day 1 if no visual symptoms are reported, and at study discontinuation. There is a +/- 7 day window allowed for eye exam at Cycle 3 day 1
5. One should aim to administer AUY922 on the same day each week, but there is a +/- 2 day window allowed to account for holidays, inclement weather, transportation difficulties, etc. For patients who are unable to tolerate the protocol-specified dosing schedule, schedule adjustments are permitted. This includes the ability to skip a week of dosing if needed up to once per cycle. Patients who continue treatment beyond progression can skip up to two infusions per cycle if needed after discussion between the treating MD and the overall PI of the study.
6. A CT scan with contrast of the chest, abdomen, and pelvis will be performed on patients at baseline (screening) -30 to -1 days prior to study drug administration. The same type of imaging modality (CT with contrast or MRI) used at screening must be used for all subsequent follow-up assessments. Follow-up CT/MRI scans will be performed every 6 weeks ( $\pm$ 7 days) from registration.

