#### 11.1.2 Data Submission

**Table 8. Schedule for completion and submission of eCRFs to the QACT**

| Form                         | Submission Timeline  |
|------------------------------|--|
| Eligibility Checklist        | Complete prior to registration with QACT                                       |
| On Study Form                | Within 14 days of registration   |
| Baseline Assessment Form     | Within 14 days of registration   |
| Treatment Form               | Within 10 days of the last day of the cycle                                    |
| Adverse Event Report Form    | Within 10 days of the last day of the cycle                                    |
| Response Assessment Form     | Within 10 days of the completion of the cycle required for response evaluation |
| Off Treatment/Off Study Form | Within 14 days of completing treatment or being taken off study for any reason |
| Follow up/Survival Form      | Within 14 days of the protocol defined follow up visit date or call            |

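### The study calendar accepts a serum pregnancy test up to 14 days before the first AUY922 dose, but eligibility criterion 3.1.8 requires it within 72 hours; the calendar footnote should be corrected to 72 hours

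*Combined protocol and SAP*

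**What the plan says.** Two places in the protocol set a time limit for the serum pregnancy test, both counted back from the first administration of AUY922.

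- **Section 3.1, criterion 3.1.8.** The test must be taken at most "72 hours prior to dosing". It applies "in all pre-menopausal women and women" less than 2 years past the onset of menopause. The same criterion states that the drug's effects on the developing fetus are not known.
- **Section 8, Table 6, footnote 3.** For women of child-bearing potential, "a serum pregnancy test must be obtained prior (within 14 days) to the first administration of AUY922".

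Three other provisions bear on which limit applies in practice.

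- **Section 4.2** says that, for registration, "the participant must meet each inclusion and exclusion criteria listed on the eligibility checklist".
- **Table 8 (Section 11.1.2)** gives the timing of that checklist: "Complete prior to registration with QACT".
- **Section 5.1.1** says: "The patient should continue to meet all eligibility criteria on C1D1, as they did during the screening period".

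**The concern.** The test, the reference dose and the mandatory force are the same in both places; only the limit differs. Table 6 has no separate row for the pregnancy test. Footnote 3 is attached to the hematology and biochemistry row, whose baseline column runs from day -21 to day -1. The footnote is therefore the only timing the calendar gives for this test, and it does not refer back to 3.1.8.

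Staff who schedule visits from the calendar could reasonably accept a result 10 days old. If that result is not refreshed, a woman is dosed who does not meet an eligibility criterion, and an older negative result is relied on when the drug is first given. That is an avoidable eligibility deviation, and a weaker screen for early pregnancy than 3.1.8 sets.

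**Working it through.** No design calculation is involved. The check compares the two limits in the same units and then asks whether any other provision settles the difference.

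**Inputs**

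| Item | Criterion 3.1.8 | Table 6, footnote 3 |
|---|---|---|
| Test | Serum pregnancy test | Serum pregnancy test |
| Counted back from | First AUY922 administration | First AUY922 administration |
| Limit | 72 hours | 14 days |
| Who is tested | Pre-menopausal women and women less than 2 years after onset of menopause | Women of child-bearing potential |

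**Arithmetic**

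- Footnote limit in hours: 14 × 24 = 336.
- Difference: 336 − 72 = 264 hours; 264 / 24 = 11 days.
- Ratio: 336 / 72 = 4.67.

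**Which tests satisfy which rule**

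| Age of the only test at first dose | 3.1.8 | Footnote 3 |
|---|---|---|
| Up to 72 hours | met | met |
| More than 72 and up to 336 hours | **failed** | **met** |
| More than 336 hours | failed | failed |

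For example, a test 10 days before dosing is 10 × 24 = 240 hours old. That is inside 336 and outside 72.

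**Does another provision resolve it?**

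1. *Registration (Section 4.2, Table 8).* Every checklist criterion must be met, but the checklist is completed before registration, and registration precedes treatment. The protocol states no maximum interval between registration and first dose. A limit counted back from dosing therefore cannot be fully verified at that point. The checklist's wording is not in the documents, so it counts neither for nor against.
2. *Cycle 1 Day 1 (Section 5.1.1).* This re-applies eligibility at dosing and so favours 72 hours. It is worded as *should*, and it neither names the pregnancy test nor asks for a repeat. A site that takes 14 days to be the valid window could conclude that the criterion is still met.
3. *Table 6, inclusion/exclusion row.* This leads the reader to the criteria, but it is marked at baseline only, and baseline extends back to day -21.

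All three point towards 3.1.8 as the governing rule. None changes what footnote 3 permits.

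**Effect on the analyses.** Sections 13.5 to 13.7 include all patients in the safety, response and survival analyses. A woman dosed on an older test would still be counted, so the two-stage rule in Section 13.2 and its error rates do not change.

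**The case against.** The strongest reply is that the two rules can be met together. A test within 72 hours satisfies both, and nothing in the footnote claims to override 3.1.8. A site following the whole protocol has one compliant course. Because the 3.1.8 window is anchored to dosing, a woman whose only test is older than 72 hours does not meet all criteria on Cycle 1 Day 1, so the need for a repeat follows from Section 5.1.1 even though it is not spelled out.

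Other protections also apply. Exclusion 3.2.7 bars pregnant women. Criterion 3.1.8 requires agreement to adequate contraception and prompt reporting of a suspected pregnancy. The remaining risk is a pregnancy missed by an earlier test, despite contraception, at a site that also overlooked 3.1.8. The 4.67 ratio is a unit conversion and does not measure harm. Finally, the documents do not say outright which window was intended.

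Most of this stands as a limit on the size of the problem. It does not remove it. The footnote presents 14 days as sufficient, and a reader of the calendar has no signal that it is not. The test is the means of finding a pregnancy that contraception did not prevent, so its timing matters even with the other protections. The choice of 72 hours is inferred, but the inference is well supported: 3.1.8 is the eligibility rule, is the stricter of the two, sits beside the statement on fetal risk, and is re-applied at Cycle 1 Day 1.

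**Conclusion.** The concern holds. Footnote 3 to Table 6 permits a pregnancy test that criterion 3.1.8 does not accept, over a range of 264 hours (more than 72 and up to 336 hours before first dose). Confidence in the mismatch is high. That 72 hours should prevail is a judgement from the structure of the protocol, since the sponsor's intent is not stated.

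The consequence is confined to patient safety and protocol compliance. It arises only if a site relies on the calendar and does not repeat the test under the Cycle 1 Day 1 re-check. How many women that would involve cannot be estimated from the documents. The sample size, the stopping rule, the error rates and the analysis populations are untouched. The correction should be made because this is an operative safety instruction and the change is trivial.

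**What to change.** Let 3.1.8 govern. Amend Table 6, footnote 3, so that the serum pregnancy test is required *within 72 hours prior to the first administration of AUY922 (repeat if the screening test is older)*, and add *see 3.1.8 for who is tested*. The cross-reference also settles the difference in wording between the footnote's women of child-bearing potential and the menopausal-status definition in 3.1.8.

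The cost is one line of amendment text. For a participant it is at most one repeat blood test, which 3.1.8 already requires.
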